8.3. Inclusion Criteria for Long-Term Extension Period

To be eligible to participate in the LTE period, participants must meet the following eligibility criteria at Week 76 or 78 and confirmed at Week 80:

1. Ability of the participant to understand the purpose and risks of the study and provide signed and dated informed consent and authorization to use confidential health information in accordance with national and local participant privacy regulations. In countries where applicable laws allow, the participant's informant/study partner and/or legally authorized representative may provide informed consent in lieu of the participant's signature (same as above in Section 8.1).

CONFIDENTIAL

The information contained herein may not be used, disclosed, or published without the written consent of Biogen MA Inc.

2. Participant must have completed the placebo-controlled period of the study, including the Week 78 Visit. Participant must have taken at least 14 doses of study treatment and not have missed more than 4 consecutive doses of study treatment. Participants who do not meet these criteria may enter the LTE period only with the Sponsor's approval.
3. All women of childbearing potential and all men with female partners of childbearing potential must practice highly effective contraception during the study and for 6 months (24 weeks) after their last dose of study treatment. For further details of contraceptive requirements for this study, see Section 15.5. Female participants should not become pregnant during the study and for 6 months (24 weeks) after their last dose of study treatment. It is recommended that male participants should not father children during their participation in the study and for 6 months (24 weeks) after their last dose of study treatment (same as above in Section 8.1).
4. Medically able to undergo the study procedures and to adhere to the visit schedule at the time of study entry into the LTE period, as determined by the Investigator. Apart from a clinical diagnosis of MCI due to AD or mild AD, the participant must be in good health as determined by the Investigator, based on medical history.
5. Must have the ability to comply with procedures for protocol-related tests.
6. Must have 1 informant/study partner who, in the Investigator's opinion, has frequent and sufficient contact with the participant (at least 10 hours/week) as to be able to provide accurate information about the participant's cognitive and functional abilities. The study partner must agree to accompany the participant to clinic visits and/or be available by phone at designated times to provide information to the Investigator and study staff about the participant (and to attend in-person clinic visits that require partner input for scale completion) and must agree to monitor the participant's administration of any prescribed medications. A study partner should be available for the duration of the study, and the participation of the same study partner for the duration of the study is encouraged. The study partner must be literate and give informed consent (same as above in Section 8.1).

8.4. Exclusion Criteria for Long-Term Extension Period

Participants will be excluded from entering the LTE period if any of the following exclusion criteria exist at Week 76 or 78 and confirmed at Week 80:

1. Any medical or psychiatric contraindication or clinically significant abnormality that, in the opinion of the Investigator, will substantially increase the risk associated with the participant's participation in and completion of the study.
2. Other unspecified reasons that, in the opinion of the Investigator or Biogen, make the participant unsuitable for the study (same as above in Section 8.2).

CONFIDENTIAL

The information contained herein may not be used, disclosed, or published without the written consent of Biogen MA Inc.

3. [REDACTED]

4. [REDACTED]

CONFIDENTIAL

The information contained herein may not be used, disclosed, or published without the written consent of Biogen MA Inc.

9. SCREENING AND RANDOMIZATION

9.1. Screening

Participants or their legally authorized representatives, in countries where applicable laws allow, must provide informed consent before any screening tests are performed (see Section 17.3).

[REDACTED]

Screening assessments, detailed in Table 1 for the placebo-controlled period, will include confirmation of diagnosis, medical history, [REDACTED], [REDACTED], and safety assessments (e.g., laboratory tests, ECG, vital sign measurements, physical and neurological examinations, serum pregnancy test for women of childbearing potential). [REDACTED]

The necessary order of the screening assessments is provided in Table 1.

During the first screening visit, under a separate (optional) initial consent process, participants can complete the cognitive scales (including the CDR, MMSE, DKEFS Category and Letter Fluency tests, DSST, Trails A, and ISLT/ISLR). This initial cognitive screening is intended to reduce the burden on participants and study sites by avoiding unnecessary testing if participants do not meet key inclusion criteria. If the participant meets inclusion criteria for the CDR, MMSE, and ISLT/ISLR, then the full consent process must be completed prior to the administration of further screening assessments. Participants may also proceed directly to the full consent process, which would allow the administration of all screening assessments.

Participant eligibility for the study will be determined during up to 3 screening visits in the approximately 9-week (65-day) Screening Period preceding randomization during the placebo-controlled period.

It is recommended that all the screening procedures for the placebo-controlled period be completed within 65 days; however, the overall Screening Period may be extended up to 90 days in consultation with the Medical Monitor in advance and provided that written documentation is received from the Sponsor or delegate ([REDACTED]). The following screening tests should be repeated if the Screening Period is >65 days: confirmation of eligibility criteria, abbreviated medical history, and physical examination. In addition, some cognitive assessments and/or safety assessments may require repeating depending on the duration of the screening window extension, in discussion with the Medical Monitor.

CONFIDENTIAL

The information contained herein may not be used, disclosed, or published without the written consent of Biogen MA Inc.

Screen failures are defined as participants who provide informed consent but are not subsequently randomized. If a participant is considered a screen failure, the reasons for exclusion must be documented in the participant’s source documents and on the screening log. A minimal set of screen failure information is required to ensure transparent reporting of screen failure participants to meet the Consolidated Standards of Reporting Trials publishing requirements and to respond to queries from regulatory authorities. Minimal information includes demography, screen failure details, eligibility criteria, and any SAEs.

Participants who fail screening for the placebo-controlled period may be rescreened once at the Sponsor’s discretion, [REDACTED]

Participants or their legally authorized representatives, in countries where applicable laws allow, who chose to participate in the LTE period must provide informed consent before any screening tests are performed (see Section 17.3). [REDACTED]

Participants who chose to participate in the LTE period can be screened at Week 76 or Week 78 per Table 1, and confirmation of eligibility will be checked at Week 80 per Table 2.

9.2. Randomization

Participants will be randomized on Study Day 1 after all screening and baseline assessments have been completed and after the Investigator has verified that the participants are eligible per criteria in Sections 8.1 and 8.2. Participants will be assigned a unique identification number that will be used on study-related documents pertaining to the participant. Any participant identification numbers that are assigned will not be reused even if the participant does not receive treatment. Rescreened participants will be assigned a new number.

Randomization will be stratified by [REDACTED], region, disease stage (MCI or mild AD), and baseline AD medication use. [REDACTED]

[REDACTED]

[REDACTED]

CONFIDENTIAL

The information contained herein may not be used, disclosed, or published without the written consent of Biogen MA Inc.

[REDACTED]

[REDACTED]

[REDACTED]

Participants who are participating in the LTE period and who were randomized to receive placebo during the placebo-controlled period will receive BIIB092 at the high dose (2000 mg) once every 4 weeks during the LTE period. Participants who were randomized to receive BIIB092 during the placebo-controlled period will continue to receive BIIB092 at the dose they were randomly assigned.

See the Study Reference Guide for details on randomization.

9.3. Blinding Procedures

This study consists of a randomized, double-blind, placebo-controlled period, followed by a dose-blinded LTE period with all participants receiving BIIB092.

During the double-blind, placebo-controlled period, all study staff who conduct participant assessments will be blinded to the participant treatment assignments. The individuals conducting the rating scale assessments should remain blinded to treatment assignment as well as to participant care management and only have access to the information necessary to carry out their responsibilities. As a placebo match is not provided by the Sponsor for the study (see Section 12.2), unblinded pharmacy staff are required to manage all aspects of study treatment receipt, dispensing, and preparation. To maintain the study blind, it is imperative that participant treatment assignments are not shared with the participants, their families, or any member of the blinded study team, either at the study site or at Biogen or its representatives, except the unblinded pharmacist (or designee), the unblinded pharmacy monitor, and the unblinded CRO or Biogen safety staff. Members of the DMC will also be unblinded.

[REDACTED]

All participants will receive infusions of study treatment at 4-week intervals during the double-blind placebo-controlled period. Those participants who are randomized to receive BIIB092 once every 12 weeks versus once every 4 weeks will receive placebo at the other 4-week dosing intervals to maintain the treatment blind. See Section 11.1 for details of the treatment regimens.

CONFIDENTIAL

The information contained herein may not be used, disclosed, or published without the written consent of Biogen MA Inc.

For the LTE period, the dose information must remain restricted. The study staff, the individuals conducting the rating scale assessments, and the Investigator should remain blinded to dose assignment and only have access to the information necessary to carry out their responsibilities. To maintain the study blind, it is imperative that dose information is not shared with the participants, their families, or any member of the blinded study team, either at the study site or at Biogen or its representatives, except the unblinded pharmacist (or designee), the unblinded pharmacy monitor, and the unblinded CRO or Biogen safety staff.

Once the clinical study report has been finalized, if unblinding will not jeopardize the results of ongoing related studies, Biogen will provide the randomization codes to Investigators, who then can inform their participants about the treatment received.

CONFIDENTIAL

The information contained herein may not be used, disclosed, or published without the written consent of Biogen MA Inc.

10. DISCONTINUATION OF STUDY TREATMENT AND WITHDRAWAL OF PARTICIPANTS FROM THE STUDY

10.1. Discontinuation of Study Treatment

A participant must permanently discontinue study treatment for any of the following reasons:

- The participant becomes pregnant. Study treatment must be discontinued immediately, and the pregnancy must be reported according to the instructions in Section 15.4.1.
- The participant withdraws consent to continue study treatment.
- The participant experiences a medical emergency that necessitates permanent discontinuation of study treatment or unblinding of the participant's treatment assignment.
- The participant experiences an AE or SAE that does not resolve or requires continued treatment that meets exclusionary criteria.
- The participant experiences a severe infusion reaction
- At the discretion of the Investigator for medical reasons.
- At the discretion of the Investigator or the Sponsor for noncompliance with the terms of the protocol.

The primary reason for discontinuation of study treatment must be recorded in the participant's case report form (CRF).

All participants who discontinue study treatment prematurely will be asked to remain in the study and continue all protocol-specified visits and procedures for the period in which they discontinued treatment (i.e., placebo-controlled or LTE). Participants who discontinue treatment during the placebo-controlled period should be encouraged to attend at least the Week 24, Week 52, and Week 78/EOS Visits and who discontinue treatment during the LTE should be encouraged to attend at least the Week 80, 104, 116, 128, 152, 156, 176, 196, 200, 224, and 226/EOS Visits, depending on when treatment was discontinued, and undergo all the scheduled procedures. At a minimum, these visits should include assessment of AEs/SAEs and concomitant medications and key clinical assessments, including at least the CDR, MMSE, ISLT, ADAS-Cog 13, ADCS-ADL, and FAQ. Participants who discontinue study treatment prematurely, regardless of the treatment period, will be asked to return to the study site for a Follow-up Safety Visit 14 weeks after receiving the last dose of study treatment. See [Table 1](#), [Table 2](#), [Table 3](#), and [Table 4](#) for the Schedule of Activities.

CONFIDENTIAL

The information contained herein may not be used, disclosed, or published without the written consent of Biogen MA Inc.

10.2. Lost to Follow-Up

Participants will be considered lost to follow-up if they repeatedly fail to return for scheduled visits and cannot be contacted by the study site.

The following actions must be taken if a participant fails to return to the study site for a required study visit:

- The study site must attempt to contact the participant and reschedule the missed visit as soon as possible and counsel the participant on the importance of maintaining the assigned visit schedule and ascertain whether the participant wishes to and/or should continue in the study.
- In cases in which the participant is deemed lost to follow-up, the Investigator or designee must make every effort to regain contact with the participant. These contact attempts should be documented in the participant's medical record.
- Should the participant continue to be unreachable, that participant will be considered to have withdrawn from the study with a primary reason of lost to follow-up.

10.3. Withdrawal of Participants From Study

Participants must be withdrawn from the study for any one of the following reasons:

- The participant withdraws consent.
- The participant enrolls into another interventional clinical study in which an investigational treatment or approved therapy for investigational use is administered.
- The participant is unwilling or unable to comply with the protocol.

The primary reason for the participant's withdrawal from the study must be recorded in the participant's CRF.

Participants who withdraw from the study prematurely are to return to the study site for an Early Termination (ET) Visit and assessments as indicated in [Table 1](#), after the reason for withdrawal is identified. For such participants, clinical efficacy assessments specified at the ET Visit are not required if the participant discontinues treatment within 3 months of the previous primary efficacy (CDR) assessment and no significant changes in cognitive status are suspected by the Investigator; the study site should notify the Sponsor in such cases. An MRI scan should be performed if withdrawal occurs ≥ 6 months after the previous MRI. Blood for biomarker analysis should be collected if the participant withdraws ≥ 4 weeks after the previous sample was collected.

CONFIDENTIAL

The information contained herein may not be used, disclosed, or published without the written consent of Biogen MA Inc.

Participants who are withdrawn from the study are also to return to the study site for a Follow-up Safety Visit 14 weeks after receiving the last dose of study treatment.

[REDACTED]

[REDACTED]

CONFIDENTIAL

The information contained herein may not be used, disclosed, or published without the written consent of Biogen MA Inc.

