⁷ All participants who discontinue study treatment prematurely will be asked to remain in the study and continue all protocol-specified visits and procedures. These participants should be encouraged to attend at least the Week 24, Week 52, and Week 78 visits, depending on when treatment was discontinued, and undergo all the scheduled procedures. At a minimum, these visits should include assessment of AEs/SAEs and concomitant medications and key clinical assessments, including at least the CDR, MMSE, ISLT, ADAS-Cog 13, ADCS-ADL, and FAQ. Participants who discontinue study treatment prematurely will also be asked to return to the study site for a Follow-up Safety Visit 14 weeks after receiving the last dose of study treatment. See Section 10.1 for details. Participants who withdraw from the study prematurely are to return to the study site for an ET Visit and ET assessments. If the withdrawn participant has discontinued treatment within 3 months of the previous primary efficacy assessment (CDR) and no significant changes in cognitive status are suspected by the Investigator, the clinical efficacy assessments specified in the ET visit are not required; the study site should notify the Sponsor in such cases. An MRI scan should be performed if withdrawal occurs ≥ 6 months after the previous MRI. Blood for biomarker analysis should be collected if the participant withdraws ≥ 4 weeks after the previous sample was collected.

See Section 10.3 for details.

⁸ Visit S3 all clinical assessments must be scheduled within 7 days before Study Day 1 or performed at Study Day 1 before randomization. The overall Screening Period may be extended up to 90 days in consultation with the Medical Monitor in advance and provided that written documentation is received from the Sponsor or delegate ().

⁹ All participants should be observed and monitored by study staff for a minimum of 1 hour after the end of an infusion. Participants who experience an AE or SAE related to BIIB092 infusion should remain at the site or be sent to an inpatient monitoring facility until the Investigator has determined that the event(s) has resolved or do not require further monitoring at the site or in an inpatient setting.

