16.4.2. Methods of Analysis

16.4.2.1. Analysis of Primary Efficacy Endpoint (Clinical Dementia Rating Scale – Sum of Boxes)

The CDR-SB is the primary efficacy endpoint. The population for the analysis of CDR-SB will be participants in the ITT population who have a baseline and at least 1 postbaseline CDR-SB score.

A mixed model with repeated measures (MMRM) will be used to analyze changes from Baseline in CDR-SB using fixed effects of treatment, time, treatment-by-time interaction, baseline CDR-SB, baseline CDR-SB-by-time interaction, region, disease stage (MCI versus mild AD), and baseline AD medication use. The correlation between repeated measures of the outcomes will be taken into consideration. The least-squares (LS) means, the differences in LS means between each treatment group versus placebo at Weeks 24, 52, and 78, 95% confidence intervals (CIs), and p-values will be presented. Changes from baseline in CDR subscores will be analyzed in a similar model. Additional details will be provided in the SAP.

The multiple comparison procedure modelling (MCP-MOD) method will be used to assess and model dose-response relationships (potential candidate models will include linear, linear-log, quadratic, maximum response [E_{max}], and logistic models as specified in Section 16.10) while controlling for multiplicity. The dose-response parameter of interest for MCP-MOD will be the LS means at Week 78 for each dose group from the mixed-effects model. Pairwise comparisons of each BIIB092 dose group versus placebo will also be conducted.

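### The waiver of the Early Termination efficacy scales is timed from stopping treatment, not from leaving the study, so a closing CDR can be skipped when the last one is up to about 28 weeks old

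*Protocol*

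**What the plan says.** Protocol Section 10.3 sends participants who withdraw early to an ET visit. It then makes the efficacy scales at that visit "not required if the participant discontinues treatment within 3 months of the previous primary efficacy (CDR) assessment", on the further condition that "no significant changes in cognitive status are suspected by the Investigator". The site should tell the Sponsor when this happens.

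Table 1 footnote 7 (placebo-controlled period) and Table 4 footnote 2 (LTE) carry the same rule, both beginning "If the withdrawn participant has discontinued treatment within 3 months of the previous primary efficacy assessment (CDR".

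Two other ET rules stand in the same paragraph of Section 10.3, and both are timed from withdrawal: "An MRI scan should be performed if withdrawal occurs ≥ 6 months after the previous MRI" and "Blood for biomarker analysis should be collected if the participant withdraws ≥ 4 weeks after the previous sample was collected".

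Section 10.1 treats stopping drug as a different event from leaving the study: "All participants who discontinue study treatment prematurely will be asked to remain in the study and continue all protocol-specified visits and procedures".

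On the analysis side, Protocol Section 16.4.2.1 limits the CDR-SB analysis to "participants in the ITT population who have a baseline and at least 1 postbaseline CDR-SB score". The LTE SAP (Section 5.3.3) adopts a treatment policy strategy and uses all observed data, including data after treatment stops. Its Section 5.3.2.1 assumes that missing data are missing at random.

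**The concern.** A waiver of this kind is meant to spare a repeat CDR when a recent one exists. Whether the last CDR is recent depends on the time from that CDR to the ET visit. The clause instead measures the time between that CDR and the end of treatment. For a participant who stops drug and leaves at once, the two dates agree. For one who stops, stays as asked, and leaves later, they do not, and nothing in the documents limits how old the last CDR may then be.

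Two things are at stake. The skipped value is off-treatment data of the kind a treatment policy analysis needs, and it can belong to an analysis visit that otherwise stays empty. The skipping is also selective. The scales remain required where decline is suspected and may be dropped where it is not, on a judgement made at withdrawal that is not a term in the SAP's MMRM.

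**Working it through.** **Inputs**
- CDR schedule (Protocol Tables 1 to 4): Screening Visit 1; Weeks 24, 52 and 78 (Days 169, 365, 547, each ±7); in the LTE, Weeks 104, 128, 152, 176, 200 and 226 (Days 729, 897, 1065, 1233, 1401, 1583).
- CDR analysis windows (LTE SAP, Appendix I, Table 1): Week 24 [2, 267]; Week 52 [268, 456]; Week 78 from Day 457; then Week 104 to Day 813, Week 128 to 981, Week 152 to 1149, Week 176 to 1317, Week 200 to 1492.
- My conventions: 3 months = 91 days = 13 weeks; treatment stop dated by the last dose; an ET CDR assigned to a window by its day. The SAP maps scheduled, EOS and unscheduled visits this way. It does not name ET separately, but ET shares the Week 78/EOS column in Table 1.

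The plan attaches no figure to this clause, so there is none to reproduce. Its sample size and power are not in question here.

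**1. Two cases that meet the timing condition**

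| Last CDR | Last dose | CDR to stop | Withdrawal | CDR to withdrawal | Window of the skipped CDR |
|---|---|---|---|---|---|
| Week 24, Day 169 | Week 32, Day 225 | 56 days = 8 weeks | Week 48, Day 337 | 168 days = 24 weeks | Week 52 |
| Week 52, Day 365 | Week 60, Day 421 | 56 days = 8 weeks | Week 76, Day 533 | 168 days = 24 weeks | Week 78 |

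In both, the stop is within 13 weeks of the CDR, so the timing condition is met. On a withdrawal clock, 24 weeks exceeds 13 and the ET CDR would be due.

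**2. Longest gap with scheduled CDRs attended**
- Week 24 to 52: 365 − 169 = 196 days, so just under 28 weeks.
- Week 52 to 78: 547 − 365 = 182 days, so just under 26 weeks.
- LTE intervals: 24 or 26 weeks.
- On a withdrawal clock: 13 weeks throughout.

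**3. Reading previous as the last CDR before the ET visit.** This does not close the gap. A participant who stops at Week 45, has the Week 52 CDR and withdraws at Week 77 stopped 52 − 45 = 7 weeks from that CDR. The timing condition is met with a CDR 77 − 52 = 25 weeks old.

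**4. Before Week 24.** The previous CDR is then the screening one. A participant who stops soon after Day 1, stays, and withdraws before Week 24 can be waived with no post-baseline CDR, and so falls outside the Section 16.4.2.1 analysis set.

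**5. Illustration of the clause's reach, on assumed timing.** Take people who stop and withdraw between the same two CDRs. Let the stop be uniform over the interval and withdrawal uniform from the stop to the next CDR. With t = 91 ÷ interval length, the share meeting the time condition is t on the treatment clock and t + (1 − t) ln(1 − t) on a withdrawal clock.
- Weeks 24 to 52: t = 91/196 = 0.464, against 0.130.
- Weeks 52 to 78: t = 91/182 = 0.500, against 0.153.

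These are shares within a subgroup whose size is unknown. They do not count lost values.

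**6. Is a 91-day withdrawal clock enough by itself?**
- On-time Week 24: 169 + 91 = 260 ≤ 267. On-time Week 52: 365 + 91 = 456 ≤ 456, with no margin.
- Week 52 CDR taken 7 days late: 372 + 91 = 463 > 456.
- LTE: 729 + 91 = 820 > 813; 897 + 91 = 988 > 981; 1065 + 91 = 1156 > 1149; 1233 + 91 = 1324 > 1317.

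A waived ET visit could therefore still fall in the next window, so a same-window condition is needed as well.

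**The case against.** Several points on the other side are sound. The clause gives permission and does not forbid the CDR. Each use should be notified to the Sponsor, so it can be traced. Earlier CDRs remain in the analysis. People who stay are asked to attend Weeks 24, 52 and 78, so the problem is confined to those who stop, stay, and leave before the next CDR or miss it. CDR-SB is the primary efficacy endpoint, but the study's primary endpoint is the incidence of AEs and SAEs. The windows, estimand and missing-data assumption cited are those of the LTE SAP. The placebo-controlled SAP is a separate document and is not among those reviewed. All of this limits the size of the problem. None of it sets a limit on the time from last CDR to withdrawal.

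It could also be said that stopping treatment is loose wording for withdrawing. The protocol does not use the terms that way: Section 10.1 separates them, and the adjoining MRI and blood rules use withdrawal. The unscheduled-visit rule in Section 11.4.1.2 also measures recency up to the visit itself. If some sites do read it loosely, practice will differ between sites, which is a further reason to correct it.

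A reader might infer that the Investigator condition should be deleted because it makes the loss selective. That would do harm. The condition only narrows the waiver. Suppose the screening CDR was 9 weeks before Day 1 (assumed) and a participant with suspected decline withdraws at Week 3, 9 + 3 = 12 weeks after it. The present text requires the ET CDR. Without the condition it would be waived, leaving no post-baseline value.

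**Conclusion.** The point holds as a mismatch between the clause and its evident purpose, and it is worth correcting. With scheduled visits attended, the last post-baseline CDR can be up to about 28 weeks old when the ET CDR is waived, against 13 weeks on a withdrawal clock. The skipped value can belong to an otherwise empty Week 52 or Week 78 window. This rests on the conventions stated in the working.

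Two stronger conclusions are tempting but not supported.
- A reader might infer a head count. The protocol's 20% dropout on 654 randomised is 131 people. With stops spread evenly over Weeks 0 to 76 and a screening CDR 9 weeks before Day 1, (4 + 13 + 13)/76 = 39.5% of stops fall within 13 weeks of the previous CDR, or about 52 people. That does not measure loss. It includes everyone who withdraws when they stop, for whom the choice of clock changes nothing. Nor is it an upper bound: a 4-week screening gap gives (9 + 13 + 13)/76 = 46%, about 60 people. The documents do not give the share who stop, stay, and withdraw more than 3 months after their last CDR.
- A reader might infer that missing at random is broken. Dropping values only where the Investigator suspects no change strains the assumption, but the documents do not show that it fails. They do not allow the size or direction of any bias in the treatment comparison to be worked out.

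**What to change.** In Section 10.3, Table 1 footnote 7 and Table 4 footnote 2, allow the ET efficacy scales to be omitted only if all of these hold:
1. the participant withdraws from the study within 3 months after the previous CDR;
2. that CDR is post-baseline and, for a withdrawal in the LTE, was done in the LTE;
3. the ET visit would fall in the same SAP analysis window as that CDR;
4. the Investigator suspects no significant cognitive change (kept as it is, as a further restriction).

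The first condition brings the clause into line with the MRI and blood rules. The second stops a screening CDR from standing in for a post-baseline one, and a Week 78 CDR from standing in for an LTE one. The third ensures that no otherwise empty window loses a value, and the selectivity left by the fourth then applies only where the window already has a CDR.

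The cost is one clause in three places, a note to sites, and a modest number of extra CDRs at ET visits that already take place. Sample size and power do not change. Because sites are already asked to notify the Sponsor of each waiver, past cases can be counted and the age of the last CDR reported for them.
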